Title: Optimizing an mHealth Intervention to Change Food Purchasing Behaviors for Cancer
Prevention
NCT04947150
Document date: 3/25/21

Protocol

Study Design

This study is a National Cancer Institute (NCI)-funded pilot, randomized controlled trial (R21CA252933) utilizing a factorial design to test the effect of four different intervention components on dietary intake and grocery store purchases. The four factors yield 16 different combinations of intervention components (Table 1). An equal number of participants were randomized to receive vs. not receive each of the four experimental intervention components. For example, half of participants have their food purchasing data monitored by a coach and half do not have this feature as part of their intervention. As another example, half of participants were randomly assigned to have household member involvement included in their intervention package, but this randomization was done independently of that for coach monitoring (i.e., the four experimental intervention components were not “bundled” together). Baseline covariates used for randomization included biological sex, body mass index (BMI), age, household size, and dietary adherence score.

Ethics Approval

This study was approved by the Drexel University Institutional Review Board (Study ID #2003007695) on March 13, 2021.

Participants, Eligibility, and Recruitment

The study enrolled 62 index participants, as well as 31 household members who are serving in a support role. Participants were recruited from the Philadelphia area in two cohorts via targeted mailings, social media outreach, and Craigslist listings, and was supported in part by community recruitment resources from Thomas Jefferson University’s Sidney Kimmel Cancer Center. Specifically, Jefferson’s Regional Liaison Office employed their “honest broker” system which aided in identifying and contacting potential participants using internal communication resources, community contacts, and other available resources (e.g., participants within the Jefferson community who matched eligibility criteria were emailed about their interest in participating). Interested individuals completed a screening survey and, if deemed preliminarily eligible, attended an information session via videoconferencing. After the session, those interested in participating attended a baseline assessment, in which their final eligibility was determined.

Index participants were required to be age 18 or older and fluent in English. In addition, participants were required to be the primary grocery shopper in their household and report shopping at stores that could passively stream item-level data from a store loyalty card to the project portal (Walmart, Target, ShopRite, or Wegmans). Inclusion criteria also included having a smartphone with an iOS or Android operating system that was compatible with the program app and living in a household with another adult who indicated willingness to participate in a support role. Exclusion criteria were as follows: medical condition or psychiatric condition (e.g., active substance abuse, eating disorder) that would be a poor match with program content or limit ability to comply with program dietary recommendations; plans to enroll in another lifestyle modification program within 6 months of program start; bariatric surgery history; pregnant or breastfeeding or plans to become pregnant in the next 6 months. All index participants provided written informed consent for participation, as did the 31 household members of index participants randomized to HH.

Intervention

Uniform components

All index participants attend a nutrition education workshop (three sessions, 90 minutes each, all delivered via videoconferencing software) focused on eating a diet consistent with WCRF/AICR guidelines. Content is organized around the key WCRF/AICR dietary recommendations: 1) eat a diet rich in whole grains, vegetables, and fruit; 2) limit consumption of highly processed foods; 3) limit consumption of red and processed meat; 4) eliminate consumption of sugar-sweetened beverages. Sessions consist of psychoeducation about these nutrition recommendations, group discussions on health behavior change (e.g., common triggers for eating behavior), didactics on behavioral skills (e.g., stimulus control, functional analysis, problem solving), and hands-on practice (e.g., reading a nutrition label). Each workshop concludes with goal setting and meal planning, where participants identify concrete guideline-related goals for the coming week, create a weekly meal plan, and begin constructing a grocery list for relevant items. They are encouraged to finish their meal plan and grocery list independently after each session. Workshop sessions consist of 10-15 participants each. Coaches are experienced in delivering lifestyle modification and have an MS or Ph.D. in psychology, nutrition, or a related field. Each participant has continuity working with the same coach for all workshop sessions and, if applicable, any additional condition-specific contacts (i.e., extra workshop sessions, coaching calls, and coach messages).

All index participants also download an app that was created for this program (Figure 2). A key feature of the app is a display of graphs that reflect how well the participant's grocery shopping purchases align with each of the program recommendations across the previous 4 weeks. Participants are encouraged to utilize these graphs to track their progress and improvement towards recommendations over time. The grocery shopping data displayed in the graphs is passively collected from participant's store loyalty accounts, as described below. During the 20-week intervention period, all participants also receive once-weekly educational messages in the app that remind them of program dietary recommendations and behavioral strategies that can promote adherence (e.g., planning, self-monitoring, goal setting). Message content includes tips for meeting program guidelines such as swapping out processed snacks for healthier alternatives, or recipe ideas to incorporate fruits and vegetables (e.g., "Replacing high-calorie, processed foods with fruits, vegetables, whole grains, beans, and legumes can help you feel fuller longer, have more energy, and better manage cravings and appetite, all of which can help you manage your weight. Identify one thing you could do this week to continue to make progress on the goal of replacing processed foods with healthier items"). These messages are standardized, such that the content in any given week's message is the same for all participants.

Experimental intervention components and contact time

As described next, the four experimental intervention components are each provided to 50% of participants, in addition to the three workshop sessions and standard weekly messages that all participants receive. The study was designed such that program contact time varies by condition, in order to evaluate the benefit of added contact time. The total number of workshop sessions ranges from 3 to 5, with 26% of participants assigned to 3 sessions (i.e., no extra workshop sessions), 48% assigned to 4 sessions (i.e., one extra workshop session),

and 26% assigned to 5 sessions (i.e., two extra workshop sessions). The total number of coach calls ranges from 0 to 9, with 18% of participants assigned to 0 calls, 29% assigned to 3 calls, 39% assigned to 6 calls, and 14% assigned to 9 calls.

As described in detail next, all participants receive one message from the app each week that includes standardized educational content, and half of participants have benefits of change content appended to the message. For half of participants, delivery of the educational app message is location-triggered. Half of participants (i.e., those who receive coach monitoring) also receive a second message in the app each week, which is written by their coach. Half of participants have a message sent to their household member each week.

Location-triggered messages

Participants randomized to receive this component receive their weekly educational message in the program app when their smartphone is within a 50-meter geofence around designated grocery stores. At baseline, participants provided information about venues where they regularly grocery shop, for geofence programming. If the system does not detect the designated location in a given week (e.g., the participant does not go to the grocery store), the app message is delivered at the end of the week. The message is only delivered once per week, even if the participant is at a grocery shopping location more than once.

Participants who are not assigned to location-triggered message delivery receive their weekly educational messages at a fixed time (i.e., Sundays at 10am), regardless of location. The content of the messages does not differ according to whether location-triggered messaging is provided or not.

Reflections on benefits of change

Participants randomized to receive the benefits of change component receive one extra 60-minute workshop session, to reflect on the anticipated benefits of purchasing healthy foods. They also attend three brief, individual coaching calls (20 minutes each) to further discuss personally meaningful benefits of change (at weeks 9, 13, and 17). Personalized content on their anticipated benefits is also added to each educational app message delivered after week 5. During the benefits of change workshop session, participants individually complete an exercise identifying short- and long-term benefits of healthy eating that are important to them, and message content is programmed according to the responses they record. (Example: “Making healthy choices today will pay off in the long run because [I will be modeling these choices for my children, and they will benefit from healthier eating as well],” where bracketed input was generated by the participant.)

Participants who do not receive the benefits of change component do not attend the additional workshop or these three coach calls focused on benefits of change, and do not receive additional message content.

Coach monitoring

For participants assigned to receive coach monitoring, the coach accesses a web-based portal where they view the participant’s food purchasing data, which is passively collected from the point of purchase using store loyalty accounts. The coach sends the participant a personalized message each week in the app, sharing feedback and observations from the food purchasing data. The participant also completes three calls with the coach (20 minutes each, held in

weeks 4, 10, and 15) designed to further enhance supportive accountability for program goals. The coach messages and calls provide reinforcement for purchases consistent with program goals (particularly those that represent a change from baseline) and express concern for areas in which adherence is low.

If a participant is not assigned to receive coach monitoring, the coach has no objective information about food purchasing and the participant does not receive any personalized coach messages in the app or phone calls focused on coach monitoring.

Household support

Participants assigned to receive household support as part of the intervention select one adult in their household to serve in the support role. This household member receives weekly text messages (Example: “Your household member is likely trying to keep up new healthy habits for meal planning and grocery shopping. Identify one thing you can do to support their efforts with these changes this week. For instance, communicating in advance about meal and snack preferences, showing appreciation, or offering to look for healthy recipes to try.”). Additionally, the index participant and household member jointly participate in one extra 60-minute workshop session and three 20-minute coaching calls focused on household support (held in weeks 7, 11, and 16). (The household member does not attend any other workshop sessions or coaching calls). The content of the workshops and calls is designed to elicit support for changing the home food environment and enhance supportive accountability by making household members aware of the index participant’s commitment to improving dietary intake.

For index participants who are not assigned to receive this intervention component, household members have no program involvement.

Measures

Feasibility and acceptability

Feasibility and acceptability data are being collected and will be compared to pre-established benchmarks. Recruitment feasibility will be operationalized with a benchmark of >5 participants enrolled per month of recruitment and $<30\%$ of those otherwise interested/eligible refusing participation. Retention feasibility will be operationalized with a benchmark of $>70\%$ of participants completing each follow-up assessment. Feasibility and acceptability of food purchasing data will be operationalized with a benchmark of $>90\%$ of participants having food purchase digital data successfully captured. Feasibility for message delivery will be assessed by location-triggered messaging delivery, with successful receipt of messages measured by $<5\%$ of delivery encountering technological problems. User-rated acceptability will be measured by the benchmark of a mean rating >28 on the Treatment Acceptability Questionnaire (adapted, 8-items; 7-point Likert scale; given at 10 and 20 weeks). Qualitative information about acceptability will be collected via post-intervention focus groups. Focus groups will be audio recorded, transcribed, with responses coded for themes and patterns, and used to further refine the intervention for future testing.

Dietary intake

All participants complete dietary intake questionnaires at 0 and 20 weeks. Cohort 1 participants completed three days of food recalls at each time point, administered by the Automated Self-

Administered 24-hour Dietary Recall (ASA24), an NCI-designed software tool [86]. ASA24 is based on the well-validated automated multiple pass method, which has been shown to be as or more accurate than nutritionist-administered 24-hour food recall when using doubly labeled water as the criterion.

After baseline administration of the ASA24, many Cohort 1 participants reported that they perceived this measure to be excessively burdensome. Due to the low acceptability, we replaced the ASA24 with the Diet History Questionnaire (DHQ-III) for Cohort 2 participants, due to its streamlined format and reduced completion time. The DHQ-III is a food frequency questionnaire developed by the NCI. The nutrient and food group database for DHQ-III is based on a compilation of national 24-hour dietary recall data from the National Health and Nutrition Examination Surveys. Cohort 2 participants completed the DHQ-III at baseline and will complete it again at 20 weeks. Given the different measures of dietary intake, differences in dietary intake variables across waves will be assessed and analyses on dietary intake will be conducted separately for each wave.

Both the ASA24 and DHQ-III provide item-level nutritional information for all food/drinks consumed as well as daily totals of various nutrient variables. For the NCI recommendation specific to highly processed food, food items will be flagged and included in this category based on those defined as highly processed based on the widely used NOVA classification system. Items in the processed food category include salty snacks, frozen and prepared meals, baked goods, dessert, fried potatoes, candy, packaged bread and buns, refined grains, breakfast cereal, processed cheese, etc. Relevant items that fall into this category are pulled from the ASA24 items-level output based on their Food and Nutrient Database for Dietary Studies (FNDDS) food code and from the DHQ-III items-level output based on their coding in the NCI's associated nutrient database and included in nutrient total calculations for processed foods. Similarly, sugar-sweetened drinks are identified in the ASA24 (based on their FNDDS food code) and DHQ-III (based on nutrient database) and used to calculate adherence to the relevant guideline. Sugar-sweetened drinks include non-diet sodas, non-diet fruit drinks, energy drinks, and sugary coffee drinks.

Average daily intake of the following items relevant to NCI dietary recommendations will be calculated from the ASA24 and DHQ-III:

1. Fiber: grams of fiber
2. Fruit and vegetables: cups of all fruit (intact whole or cut fruit not including fruit juices) and vegetables (all vegetables excluding starches)
3. Added sugar from processed food: grams of added sugar consumed from items flagged as highly processed (as described above)
4. Saturated fat from processed food: grams of saturated fat consumed from items flagged as highly processed (as described above)
5. Sodium from processed food: milligrams of sodium consumed from items flagged as highly processed (as described above)
6. Red meat: ounces of beef, veal, pork, lamb, and game meat
7. Processed meat: grams of frankfurters, sausages, corned beef, and luncheon meat made from beef, pork or poultry
8. Sugar-sweetened drinks: ounces of sugar-sweetened beverages (as defined above)

Given that NCI dietary recommendations for red and processed meat are on the week (vs. daily) level, average daily intake of red and processed meat are prorated to reflect intake over 7 total days.

Scores for adherence in each domain of the NCI dietary recommendations are calculated based on the 0, 0.5, 1 cutoff values established previously, where 1 reflects fully meeting the recommended level of intake, 0.5 indicates partially meeting recommended levels, and 0 reflects failure to meet the recommendation. When guidelines include multiple sub-categories (e.g., fiber and fruits/vegetables), the guideline score was calculated as the average of adherence on sub-categories. Two overall adherence scores were calculated: 1) the sum of adherence on the four guidelines (range 0-4) and 2) average adherence on the four guidelines (range 0-1). The subscores are: a) average of adherence scores for fiber and fruits/vegetables, b) average of adherence scores for added sugar, saturated fat, and sodium in processed foods, c) average of adherence scores for red and processed meats, and d) adherence score for sugar-sweetened drinks.

As a secondary outcome for dietary intake, an adapted, 13-item Food Frequency Questionnaire is administered at baseline and 20 weeks. Each item pertains to one of the four dietary guidelines (e.g., “Whole grain products or high fiber starches”, “Red meats such as beef, pork, lamb”, “Non-diet sweet drinks”), and participants are instructed to report the frequency with which they ate the foods in the past month with a 6-point Likert-type scale (ranging from 0 - “never” to 5 - “twice or more per day”). Total guideline scores will be calculated as the average of responses to all items pertaining to that guideline (e.g., guideline 1 as the average of 0-5 response for fiber and 0-5 response for fruits/vegetables).

Mediators

Consistent with the study’s conceptual model, three potential mediators are measured. An adapted Goal Salience Questionnaire is administered at each time point (baseline, 10, and 20 weeks) to measure dietary goal salience, i.e., the extent to which participants think about dietary recommendations when grocery shopping. Motivation for dietary adherence is measured with items adapted from the Treatment Self-Regulation Questionnaire [98] at each time point. Two measures of household social factors are administered at baseline, 10 weeks, and 20 weeks, where items were adapted to apply to one’s household rather than social network more broadly: Supportive Accountability Questionnaire and Sallis Social Support for Diet.

Moderators

Several potential moderators were measured at baseline. Participants completed a self-report demographics questionnaire that gathered information about sex, race, ethnicity, age, education level, household size, and grocery shopping frequency. To measure the quality of the relationship between the index participant and their household member, an adapted version of the Relationship Assessment Scale [103] was administered. Weight, height, and weight history were measured using an investigator-developed weight history questionnaire. Uncontrolled eating, cognitive restraint, and emotional eating were measured with a 21-item

version of the Three Factor Eating Questionnaire-R21 (TFEQ-21-item version) at baseline. The TFEQ will be completed at 10 and 20 weeks as well.

Household Member Information

Participating household members are administered the following questionnaires, which will be examined in exploratory analyses: an investigator-developed household demographics and goals questionnaire (at baseline only), the adapted Food Frequency Questionnaire (same instrument administered to index participants, at baseline and 20 weeks), and the Treatment Acceptability Questionnaire (same instrument administered to index participants, at 20 weeks).

Grocery store purchases

Beginning four weeks before intervention start date and continuing until four weeks after intervention end date, study software, utilizing an application programming interface (API), will continuously collect each participant's item-level food purchases to objectively measure how grocery shopping changes over time. Participants provided store account credentials for loyalty programs at one or more of the four designated stores (Wegmans, ShopRite, Target, and/or Walmart) to the study team at baseline. The API links item-level food purchases with nutrition databases (e.g., FNDDS) to create summary nutrition variables, including added sugar, sodium, and saturated fat from processed foods for each item in a grocery trip. Change in purchase amounts in each nutrition category of interest related to NCI guidelines (e.g., ounces of sugar sweetened beverages purchased per week) will be calculated. This will be an exploratory outcome because this method of data capture and categorization of grocery purchases is novel, and feasibility has not yet been tested.

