Title: Optimizing an mHealth Intervention to Change Food Purchasing Behaviors for Cancer
Prevention
NCT04947150
Document date: 3/25/21

Statistical Analyses

We will run repeated measures ANOVAs that examined whether outcomes change across time (i.e., from baseline to post-treatment). Models also include the interaction effects of each intervention component (location triggered messaging, benefits of change, coach monitoring, and household support) and time to determine whether these components could enhance change. Each condition variable is coded as 0=OFF or 1=ON, and all conditions are included in a single model for each outcome. We also report and interpret effect sizes (partial eta squared; η^2) in addition to *p*-values. Effect sizes are interpreted as meaningful if they are .06 or higher, indicating a medium effect. Post-hoc pairwise comparisons examine change in each guideline across time separately for each condition.

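### Five baseline covariates were used in the randomization but none is in the SAP model; if they were balanced and predict change, component tests are conservative and partial eta squared is pulled down

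*Protocol*

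**What the plan says.** The Protocol (Study Design) describes a four-factor design with 16 combinations and says: "An equal number of participants were randomized to receive vs. not receive each of the four experimental intervention components". It then adds: "Baseline covariates used for randomization included biological sex, body mass index (BMI), age, household size, and dietary adherence score". It does not say how the covariates were used (stratification, minimisation or another scheme). On sample size: "The study enrolled 62 index participants, as well as 31 household members who are serving in a support role".

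The SAP is one paragraph (Statistical Analyses). Its analysis is: "We will run repeated measures ANOVAs that examined whether outcomes change across time (i.e., from baseline to post-treatment"). On terms: "Models also include the interaction effects of each intervention component (location triggered messaging, benefits of change, coach monitoring, and household support) and time". The four condition variables are coded 0/1 and "all conditions are included in a single model for each outcome". No baseline covariate is named. The SAP reports p-values and partial eta squared, with this rule: "Effect sizes are interpreted as meaningful if they are .06 or higher, indicating a medium effect". It states no significance level and plans no confidence intervals.

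Under Dietary intake, the Protocol explains that Cohort 1 used ASA24 and Cohort 2 used DHQ-III, so "analyses on dietary intake will be conducted separately for each wave". The same section defines an overall dietary adherence score as an outcome, and the Protocol describes no other score of that name.

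**The concern.** When allocation is constrained to balance covariates, the chance ON/OFF differences they would have caused are largely removed from the estimated component effect. A model that omits them still counts their contribution as residual error. The reported standard error then describes a looser randomization than the one carried out. The estimate is not biased, but the test rejects too rarely.

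The aim is to find which of four components enhance change, with 62 people and dietary analyses split by wave. At that size, the cost of an overstated standard error is a useful component passed over, either on its p-value or because partial eta squared falls short of .06.

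The relevant share of variance is in change, not in level. With two time points, the component-by-time test is a test on change scores, so stable differences between people by sex, age, BMI or household size already cancel.

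**Working it through.** The documents contain no power or error-rate figure to reproduce. One allocation check is possible. The Protocol's workshop-session percentages (26/48/26) fit 16, 30 and 16 of 62. The coach-call percentages (18/29/39/14) fit 11, 18, 24 and 9. The first set gives 30 + 2×16 = 62 = 2×31 assignments, and the second gives 18 + 2×24 + 3×9 = 93 = 3×31. Both fit 31 people ON per component. They say nothing about covariate balance.

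**Inputs**
- From the documents: n = 62, four 1:1 components, five allocation covariates, two time points, and a retention benchmark above 70% (Feasibility and acceptability).
- Assumed: R², the share of variance in change that the five covariates explain; ρ, the baseline to week-20 correlation; a wave of 31 (cohort sizes are not given); the allocation scheme; and a 5% level.

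**Closed form under perfect balance**
- Standard error overstated by 1/√(1−R²).
- True level = 2[1 − Φ(1.96/√(1−R²))].
- At R² = 20%: 1/√0.8 = 1.118, and 1.96 × 1.118 = 2.19, giving a level of 2.8%.

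**Simulated level of the unadjusted test** (nominal 5%; 1,500 trials × 4 component tests per setting; Monte Carlo SE about 0.3 points)

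| R² | Perfect balance | Minimisation, n=62 | Rerandomization, n=62 | Minimisation, n=31 | Rerandomization, n=31 |
|---|---|---|---|---|---|
| 0 | 5.0% | 5.0% | 5.6% | 4.9% | 4.5% |
| 10% | 3.9% | 4.2% | 4.4% | 4.5% | 3.8% |
| 25% | 2.4% | 2.8% | 2.7% | 3.4% | 2.8% |
| 50% | 0.6% | 1.8% | 1.0% | 2.3% | 1.0% |

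With the five covariates added, the level is 4.7 to 5.5% in every balanced setting. Under simple randomization the unadjusted level is 4.8 to 5.6%, so the effect comes from the balancing. A separate simulation, taking the best balanced of 60 random allocations, gives 3.6% at n=62 and 3.4% at n=31 when R² = 20%.

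**The dietary adherence score as outcome.** With equal variances at the two times, baseline explains R² = (1−ρ)/2 of the variance in change. Under perfect balance on that score, the level is 4.4% at ρ = 0.9, 3.4% at 0.7, 2.4% at 0.5 and 1.5% at 0.3. Having baseline as the time-0 response does not correct this, because a change score fixes the coefficient on baseline instead of estimating it.

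**The .06 rule.** Take a component whose adjusted partial eta squared is .06, so its ratio to error is .06/.94 = .0638. With good balance and R² = 25%, omitting the covariates enlarges the error term: .0638 × .75 = .0479, and .0479/1.0479 = .046. The component drops below the threshold.

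**What the five-covariate model gains or costs** (best of 60 allocations; power for an assumed effect of 0.7 SD of change in brackets; dropout at random)

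| Analysed | R² = 0 | R² = 10% | R² = 20% |
|---|---|---|---|
| 62 of 62 | 2% wider | 3% narrower (78→79%) | 9% narrower (79→84%) |
| 43 of 62 | 5% wider (60→55%) | unchanged (59→60%) | 6% narrower (61→65%) |
| 31 of 31 | 6% wider | neutral | 6% narrower |
| 22 of 31 | 16% wider (30→26%) | 8–9% wider (32→28%) | 3% wider (31→32%) |

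Error degrees of freedom are n − 5 without the covariates and n − 10 with them: 57 to 52 at 62, 26 to 21 at 31, and 17 to 12 at 22.

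**The case against.** The strongest reply is that everything depends on two things the documents do not give: how tightly allocation was balanced, and whether the five factors predict change. That stands. A reader might infer that the component tests do run below 5% and that the planned intervals are too wide. The documents do not support that as fact. At R² = 0 the level is 5%, and the SAP states neither a 5% level nor any intervals.

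A reader might also argue that household size obviously drives purchase amounts. That concerns level. The Protocol (Grocery store purchases) analyses change in purchase amounts, and nothing in the documents shows that household size predicts change.

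Nor do the documents say which outcomes are pooled over all 62. The food frequency questionnaire is called a secondary outcome for dietary intake, so the split by wave may apply to it, although the reason given for the split is the differing instruments. Purchases are exploratory.

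It can also be said that five covariates are too many for a per-wave model. That stands: with 22 completers, adjustment costs precision throughout the range from 0 to 20% explained.

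Finally, the error is conservative and the trial is a pilot. Both are true, and they limit the weight of the point. They do not remove it, because selecting components is the purpose and the covariates are already in hand.

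**Conclusion.** The mismatch is real, and nothing else in the documents repairs it. Its effect is conditional. If balance was achieved and the factors explain 20% of the variance in change, the true level is about 3 to 4% at the conventional 5%; at 10% explained it is about 4%; at zero there is no loss.

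The firmest case is the adherence score. The test on it is conservative if the score was balanced and ρ is below 1, taking the variances at the two times as equal.

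This does not make the plan conservative overall. With 31 per wave, the .06 rule still flagged a null component in about 9 to 22% of simulated tests under the balanced schemes. The conservatism concerns the p-value. There is no bias and no inflation of false positives in that test, so this is an inexpensive improvement and does not invalidate the analysis.

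**What to change.** - State in the SAP how the five covariates entered the randomization, and which outcomes are analysed on all 62 participants.
- In those pooled models, add the five covariates, each crossed with time. Centre the continuous ones, and centre the adherence score within cohort because the two cohorts used different instruments.
- In the per-wave dietary models, add only the baseline dietary adherence score. Where that score is the outcome, use ANCOVA on the week-20 value. Report the five-covariate model as a sensitivity analysis.
- Report the unadjusted model as a sensitivity analysis throughout.

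**Cost.** The change is to SAP wording only, since the variables were collected at baseline. Pooled models lose five error degrees of freedom (57 to 52 with full retention). If the covariates explain nothing, intervals are about 2% wider at full retention and about 5% wider at 70% retention. Per-wave models lose one degree of freedom (26 to 25 in an assumed wave of 31).

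### Does the acceptability benchmark of 28 need its item coding, score range and deciding time point written into the plan?

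*Protocol*

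**What the plan says.** In the protocol, under Measures, Feasibility and acceptability, the trial lists benchmarks fixed in advance for recruitment, retention, capture of purchase data, message delivery and user-rated acceptability. The last of these is a "mean rating >28 on the Treatment Acceptability Questionnaire (adapted, 8-items; 7-point Likert scale; given at 10 and 20 weeks"). Acceptability is also explored in focus groups after the intervention, and those are used to refine the programme.

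Three other places bear on the point:

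- The retention benchmark in the same paragraph names its occasions; it concerns the share "of participants completing each follow-up assessment".
- Under Household Member Information, household members complete "the Treatment Acceptability Questionnaire (same instrument administered to index participants, at 20 weeks"), and their questionnaires are assigned to exploratory analyses.
- The SAP, Statistical Analyses, describes repeated measures ANOVAs of change over time and of each component's interaction with time. It does not mention acceptability.

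**The concern.** Two things appear to be left open.

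The first is the scale. Without the item coding, a reader cannot place 28 on it. Under one common coding of a 7-point item it lies below neutral, and under another it lies above, so a report that the benchmark was met could describe either a lukewarm or a mildly favourable sample. The questionnaire is adapted, so the scoring of its parent version may not carry over.

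The second is the occasion. The instrument is given twice, and the benchmark sentence does not say in so many words which administration decides. Week 10 is halfway through a 20-week programme, so the two ratings reflect different exposure. If one mean fell above 28 and the other below, the result could in principle be chosen after the ratings were seen.

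At stake is the meaning of the only numeric user-rated acceptability criterion in the trial.

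**Working it through.** **Inputs.** Threshold 28 (strictly exceeded), 8 items, 7 response points, weeks 10 and 20: protocol, Feasibility and acceptability. Index participants, 62: protocol, Participants, Eligibility, and Recruitment. Item coding: not given, so each plausible coding is tried. The documents give no derivation of 28, so there is no calculation of theirs to reproduce.

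**1. Sum or item mean?** The largest possible item mean is 7 (coded 1 to 7) or 6 (coded 0 to 6). Neither reaches 28, so the score is a sum over items. Per item, 28 / 8 = 3.5.

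**2. Where 28 sits.** For 8 items coded lo to hi, the range is 8 × lo to 8 × hi and the midpoint is 8 × (lo + hi) / 2.

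| Coding | Range | Midpoint | 28 minus midpoint | Position in range |
|---|---|---|---|---|
| 1 to 7 | 8 to 56 | 32 | −4 | (28 − 8) / 48 = 41.7% |
| 0 to 6 | 0 to 48 | 24 | +4 | 28 / 48 = 58.3% |
| −3 to +3 | −24 to 24 | 0 | +28 | unreachable |

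The third coding is ruled out because its maximum, 24, is below the threshold. Of the first two, a respondent who chooses the middle option throughout scores 32 under 1 to 7 and exceeds 28, but scores 24 under 0 to 6 and does not.

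**3. How much the coding matters for a neutral sample.** Assume SDs of 6 to 10 and n from 44 (about 70% of 62; 0.70 × 62 = 43.4) to 62. None of these SDs is in the documents. The chance that the sample mean exceeds 28 is 1 − Φ((28 − μ) / (SD / √n)). In the least decisive case, SD 10 and n 44, the standard error is 10 / √44 = 1.51.

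- Coded 1 to 7, μ = 32: 1 − Φ(−4 / 1.51) = 0.996.
- Coded 0 to 6, μ = 24: 1 − Φ(4 / 1.51) = 0.004.

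So the coding settles the interpretation almost completely, and the coding is a property of the form.

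**4. Can the coding be inferred from elsewhere?** The adapted Food Frequency Questionnaire has a stated zero-based coding: frequency "in the past month with a 6-point Likert-type scale (ranging from 0" upwards. That zero stands for never eating a food. It is a different instrument with a natural zero, and it says nothing about how an acceptability item is scored.

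**5. Which occasion?** The two administration times stand in the same sentence as the threshold, with nothing to single out one of them. The natural reading is that each mean is compared with 28. Exposure does differ by week 10, as the call schedules show:

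- Benefits of change: calls "to further discuss personally meaningful benefits of change (at weeks 9, 13, and 17"), so 1 of 3 by week 10.
- Coach monitoring: "weeks 4, 10, and 15) designed to further enhance supportive accountability for program goals", so 2 of 3 if the week-10 call is counted.
- Household support: "three 20-minute coaching calls focused on household support (held in weeks 7, 11, and 16"), so 1 of 3.

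That makes 4 of 9 calls by week 10, but only for someone assigned all nine. The protocol puts that group at 14% (0.14 × 62 = 8.7, about 9 people); 18% have no calls. The tally adds little to the plain fact that week 10 is mid-programme.

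**6. Whose ratings?** Household members complete the instrument at 20 weeks only. The benchmark's schedule of 10 and 20 weeks therefore fits index participants alone.

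**The case for a change.** The strongest case for a change is that stating the range may not be enough. If the items are coded 1 to 7, four answers of 4 and four of 3 give 4 × 4 + 4 × 3 = 28, so a sample slightly on the unfavourable side of neutral could still exceed the benchmark. On that view the threshold itself needs a rationale or a higher value. The retention benchmark also shows that the authors could name occasions when they wished to, and a sentence on coding and timing would cost almost nothing.

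Part of this stands. The coding, the range and the fact that the score is a sum are indeed not written down, and the coding governs what meeting 28 means. If it proves to be 1 to 7, the report should give the reason for 28 and should not present passing it as a favourable rating in itself.

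The step to changing the plan does not stand. The case against 28 depends wholly on an assumed coding; under 0 to 6 the same value is above neutral. Data were already being collected when the text was written, so moving a benchmark set in advance would create a problem of its own. Equally, the documents cannot certify 28 as sound. No decision rule is attached to it: the protocol says only that results will be compared with the benchmarks.

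**Conclusion.** The omission is real but is one of detail, and no change to the plan follows. Depending on a coding the documents do not give, 28 lies 4 points below or 4 points above the scale midpoint, so they show no error in it. The questionnaire form, which is not among the documents, would supply the coding. The sentence itself points to both administrations, and the household schedule points to index participants.

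An analyst with the form would report the 10-week and 20-week means for index participants against 28, with the scale range beside them. That removes both the ambiguity and any scope to pick an occasion afterwards. The consequence is confined to the wording of one descriptive pilot result; the dietary analyses in the SAP are unaffected.

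This conclusion rests on two assumptions: that the form fixes the item coding, and that higher scores mean greater acceptability, as the direction of the threshold implies. The pass probabilities rest on assumed SDs and sample sizes, but the position of 28 relative to each midpoint does not.
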